### **3.7. Rationale for Primary Endpoint**

The primary endpoint for this study is change in CD8+ T cell infiltration. Several studies have demonstrated influx of CD8+ T cells as demonstrating immunologic recognition and targeting, and as an early surrogate for treatment response. For example, one study demonstrated that expression of CD8 in early on-treatment biopsies was completely non-overlapping in responders compared with non-responders. Thus, this metric can serve as an accurate surrogate of immunologic recognition and tumor responses, and is likely more reliable than a metric such as complete pathologic response, particularly in the setting of bulky tumors that may require additional time for complete regression. In addition, in this signal finding phase II study, we are evaluating two arms with likely active treatments in parallel, rather than comparing these interventions. Sample size is further based on doubling of CD8+ T cell infiltration from analysis of responding patients in two studies, with a standard deviation of 1000.

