## **4. OBJECTIVES AND ENDPOINTS**

Objectives	Endpoints

Primary
 

• To evaluate the efficacy, measured by change in activated GZMB+ CD8+ T-cell density intratumorally, of two immunotherapy regimens in patients with advanced melanoma: nivolumab plus relatlimab in patients with MHC-II (+) melanoma; and nivolumab plus ipilimumab in patients with MHC-II (-) melanoma.

	

• Change in activated GZMB+ CD8+ T-cell density intratumorally.

Secondary
 

• To evaluate the response rate, median progression free survival, overall survival, and safety and tolerability of nivolumab and relatlimab in patients with MHC-II (+) melanoma; and of nivolumab plus ipilimumab in patients with MHC-II (-) melanoma.

	

• Response rate (RR)

• Median progression free survival (mPFS)

• Median overall survival (mOS)

• Adverse events, clinical laboratory values, vital signs, ECGs, and other safety biomarkers.

Exploratory
 

• To explore potential associations of biomarkers with clinical efficacy and/or incidence of adverse events due to study drug by analyzing biomarker measures within the peripheral blood and tumor microenvironment.

	

• Automatic quantitative analysis (AWUA), single cell RNA sequencing, mass cytometry, T-cell receptor sequencing, germline DNA/HLA haplotyping.

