### **18.2. Sample Size and Power**

The primary endpoint for this study is change in GZMB+ CD8+ T cell infiltration. A total sample size of 36 with 18 in each arm will provide 83% power to detect a difference in mean activated CD8+ T cell density change of one standard deviations (e.g., 1 SD=1000 counts/mm^2 is roughly the effect size for doubling T cell count), with a two-sided significance level of 0.05. Assuming a 10% dropout rate, a total number of 40 patients is planned for enrollment in the study to ensure the study has adequate statistical power for the primary analysis.

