### **18.4. Statistical Analysis Plan**

Patient demographics/other baseline characteristics will be listed by patient and/or summarized descriptively by each arm. Categorical data will be presented as frequencies and percentages. For continuous data, summary statistics will be presented. Between-group differences will be assessed with t-test based on a continuous variable. Nonparametric counterparts, Wilcoxon rank sum test, will be used when assumptions for parametric methods are not met. Binary and categorical data will be analyzed with chi-squared test or Fisher's exact test. Multivariable analysis will be performed using linear regression model, where the outcome variable is the density of activated CD8+ T cell post-treatment and the explanatory variable is the MHC-II status, adjusted for baseline T cell density. Median PFS and median OS will be estimated with 95% confidence intervals. If the median has not be reached by the end of the follow-up, mean survival will be reported instead. Kaplan-Meier curves will be constructed by MHC-II status. Multiple comparison issues will be corrected using the Bonferroni's approach. All statistical analysis will be performed using R 3.4.2 or a newer version.

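### The Bonferroni rule in 18.4 has no defined scope: the 83% power stands for a single primary test, but the rule as written is needlessly severe for the exploratory high-dimensional assays

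*Combined protocol and SAP*

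**What the plan says.** **Primary test.** Section 18.2 names one endpoint ("The primary endpoint for this study is change in GZMB+ CD8+ T cell infiltration") and one powered contrast. The effect sought is a "difference in mean activated CD8+ T cell density change of one standard deviations". On the size of the trial, 18.2 says: "A total sample size of 36 with 18 in each arm will provide 83% power". The calculation is made "with a two-sided significance level of 0.05", and no adjusted level appears in 18.2.

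**Multiplicity.** Section 18.4 closes its list of methods with "Multiple comparison issues will be corrected using the Bonferroni's approach". It does not say which comparisons form the family, how many there are, or whether the primary or the exploratory analyses belong to it. The same paragraph lists a t-test with a Wilcoxon rank sum test as fallback, chi-squared or Fisher tests for categorical data, and a regression of post-treatment density on MHC-II status adjusted for baseline density.

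**Secondary.** Section 18.3 treats survival descriptively within each arm.

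**Exploratory.** Section 4 lists, among other assays, "single cell RNA sequencing, mass cytometry, T-cell receptor sequencing". It gives no count of features or tests. Section 18 describes no analysis and no multiplicity method specific to these assays, so the Bonferroni sentence is the only rule available for them.

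**The concern.** A multiplicity rule without a stated scope leaves two things open.

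The first is the level of the primary test. If someone counted that test into a Bonferroni family, its level would drop below the 0.05 used in 18.2 and its power below 83%. The plan should not leave that choice until the data are in.

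The second is the exploratory objective, which is to find candidate associations in high-dimensional data. Bonferroni controls the chance of even one false positive across the whole set. With thousands of features and 18 patients per arm, the threshold becomes so strict that most real effects of moderate size would be missed. That degree of protection suits confirmatory claims. It is poorly matched to a search for leads to be tested later.

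**Working it through.** **Inputs from the documents.** 18 evaluable patients per arm, a standardised difference d = 1, two-sided level 0.05, stated power 83% (all 18.2), and the Bonferroni rule (18.4).

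**Inputs assumed.** The number of tests k in a Bonferroni family, the number of exploratory features, the share of features that truly differ, the size of the true differences (1 or 1.5 SD), and independence between features. The documents give none of these. The exploratory comparison is taken as 18 against 18. That is the most favourable two-group split of 36 patients, so a split by response or by adverse event could do no better.

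**Step 1: reproduce the plan's figure.** For a two-sample t-test, degrees of freedom = 2 × 18 − 2 = 34, and the non-centrality parameter = d × √(n/2) = 1 × √9 = 3.0. The two-sided 0.05 critical value on 34 df is 2.032. The probability that a non-central t with parameter 3.0 falls beyond ±2.032 is 0.830. The stated 83% is therefore the power of one unadjusted two-sample t-test (k = 1).

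**Step 2: what would change it.** Replacing 0.05 by 0.05/k in the same formula gives:

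| k (assumed) | Level | Power at 1 SD |
|---|---|---|
| 1 | 0.05 | 83.0% |
| 2 | 0.025 | 74.1% |
| 3 | 0.0167 | 68.4% |
| 5 | 0.01 | 60.9% |
| 10 | 0.005 | 50.8% |

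Only the first row corresponds to anything in the documents. The others show what would follow if the primary test were put in a family of that size.

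**Step 3: exploratory features under Bonferroni.** The same formula is used, with k equal to the number of features; the non-centrality parameter is 3.0 at 1 SD and 4.5 at 1.5 SD:

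| Features (assumed) | Per-feature level | Power at 1 SD | Power at 1.5 SD |
|---|---|---|---|
| 100 | 0.0005 | 22.9% | 73.2% |
| 1,000 | 0.00005 | 8.0% | 46.4% |
| 20,000 | 0.0000025 | 1.5% | 18.1% |

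**Step 4: compare with Benjamini-Hochberg.** This procedure orders the m p-values and rejects all up to the largest rank i for which p(i) ≤ q × i/m, where q is the chosen false discovery rate. Power was simulated with independent t statistics on 34 df and true effects of 1 SD:

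| Setting (assumed) | Bonferroni, 5% family-wise | Benjamini-Hochberg, q = 5% | Benjamini-Hochberg, q = 10% |
|---|---|---|---|
| 20,000 features, 2% true | 1.5% | 14% | 23% |
| 20,000 features, 5% true | 1.5% | 26% | 39% |
| 40 markers, 20% true | 32.5% | 53% | 67% |

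The q = 5% column uses the same nominal figure as Bonferroni, although the error rate it controls is a different one. The further gain at 10% comes from accepting a looser level.

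**Step 5: in counts.** With 20,000 features and 5% true there are 1,000 real differences. Bonferroni would find about 0.015 × 1,000 = 15. Benjamini-Hochberg at 5% would find about 0.26 × 1,000 = 260, with about 260 × 0.05/0.95 ≈ 14 false leads beside them. At 10% it would find about 390, with about 390 × 0.10/0.90 ≈ 43 false leads. With 40 markers and 8 true, the expected finds are 0.325 × 8 = 2.6, 0.53 × 8 = 4.2 and 0.67 × 8 = 5.4.

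**The case against.** The strongest case on the other side concerns the primary test. A reader might infer that Bonferroni applies to it, so that 83% is not the power of the test that will be run. The documents do not support that:

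- Section 18.2 has one primary endpoint and one contrast, and correcting a single comparison leaves 0.05 unchanged.
- The Wilcoxon test replaces the t-test when its assumptions fail. It is not a second test.
- The chi-squared and Fisher tests concern other data, and survival is descriptive.
- The regression addresses the same contrast with baseline adjustment.
- The primary objective covers two regimens, and Section 3.7 disclaims a comparison between them. That might suggest two within-arm claims at 0.025 each. But 18.4 plans no within-arm test, and the tension between 3.7 and 18.2 concerns what is being estimated. It does not show that two Bonferroni tests are planned.

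This part of the objection stands.

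On the exploratory side, it can be said that the sentence never mentions those assays, that the feature counts and effect sizes are not in the documents, and that markers can be ranked by effect size and interval without any test. It can also be said that Bonferroni is conservative, not invalid. All of that is fair, and it rules out the claim that the exploratory objective is unachievable: with about 100 features and effects of 1.5 SD, power under Bonferroni is 73%. It does not remove the point. The sentence has no exclusion, nothing else in Section 18 governs these assays, and at 1 SD the cost is already large at 100 features. Leaving exploratory results unadjusted and labelled as such would also be defensible, but the plan does not say that either.

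**Conclusion.** The concern holds in a limited form. The 83% in 18.2 is reproduced exactly and stands for a single two-sample t-test at two-sided 0.05. For the primary test the gap is one of missing detail: the plan does not state that the test lies outside the Bonferroni rule, and it does not say whether the t-test or the baseline-adjusted regression is primary.

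The substantive part is exploratory. Applied as written, Bonferroni is a poor match for the assays in Section 4. It leaves roughly 1.5% to 23% power per feature at 1 SD across 20,000 down to 100 features, and 18% to 73% at 1.5 SD. In the settings examined, Benjamini-Hochberg at the same nominal 5% raises power from 1.5% to 14% to 26% (20,000 features) and from 32.5% to 53% (40 markers). These sizes depend on the assumed feature counts, shares of true effects and independence. The direction does not, because at the same nominal level Benjamini-Hochberg rejects everything that Bonferroni rejects. This is a cheap improvement to the plan and does not threaten the primary analysis.

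**What to change.** Replace the multiplicity sentence in 18.4 with text to this effect:

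- **Primary.** The primary analysis is one between-arm test, named as such, at two-sided 0.05 without adjustment, consistent with 18.2. The t-test on change is the analysis that the 83% describes. If the baseline-adjusted regression is chosen instead, say so and treat the t-test as supportive.
- **Exploratory.** Within each assay panel, features are tested with Benjamini-Hochberg control of the false discovery rate at a level fixed in advance (5% or 10%), and the results are labelled hypothesis-generating.
- **Anything else.** If Bonferroni is still wanted for some other set of comparisons, name the set and the number of tests in it.

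The cost is a few lines of SAP wording. No patients, visits or samples are added, and the sample size and the 83% do not change. The downside is that a stated share of the exploratory findings, about 5% or 10% on average according to the level chosen, will be false leads. The label makes that plain to readers.

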### ***Cockcroft-Gault Formula***

The following may be used for calculating the estimated creatinine clearance rate (e $C_{CR}$ ) using the Cockcroft-Gault formula. Additionally, the use of on-line calculators or formulas which are institutional standards for e $C_{CR}$  and differ slightly may also be used consistently throughout the study. The calculations and results must be documented in the patient's chart or research record.

When serum creatinine is measured in mg/dL:

$$eC_{CR} = \frac{(140 - \text{Age in years}) \cdot \text{Weight (in kilograms)} \cdot [0.85 \text{ if Female}]}{72 \cdot \text{Serum Creatinine (in mg/dL)}}$$

When serum creatinine is measured in  $\mu\text{mol/L}$ :

$$eC_{CR} = \frac{(140 - \text{Age in years}) \cdot \text{Weight (in kilograms)} \cdot \text{Constant}}{\text{Serum Creatinine (in } \mu\text{mol/L)}}$$

Where Constant is 1.23 for men and 1.04 for women.

**APPENDIX 2**  
***ECOG Performance Status***

Grade	ECOG Performance Status
0	Fully active, able to carry on all pre-disease performance without restriction.
1	Restricted in physically strenuous activity but ambulatory and able to carry out work of a light or sedentary nature, e.g., light house work, office work.
2	Ambulatory and capable of all self-care but unable to carry out any work activities. Up and about more than 50% of waking hours.
3	Capable of only limited self-care, confined to bed or chair more than 50% of waking hours.
4	Completely disabled. Cannot carry on any self-care. Totally confined to bed or chair.
5	Dead.

---

**APPENDIX 3**  
***New York Heart Association (NYHA) Functional Classification***

NYHA Class	Symptoms
I	No symptoms and no limitation in ordinary physical activity, e.g. shortness of breath when walking, climbing stairs etc.
II	Mild symptoms (mild shortness of breath and/or angina) and slight limitation during ordinary activity.
III	Marked limitation in activity due to symptoms, even during less-than-ordinary activity, e.g. walking short distances (20–100 m). Comfortable only at rest.
IV	Severe limitations. Experiences symptoms even while at rest. Mostly bedbound patients.

Abbreviations: NYHA = New York Heart Association

## **APPENDIX 4**

### ***Acceptable Contraception***

**For purpose of this study, acceptable birth control methods that can achieve a failure rate of less than 1% per year when used consistently and correctly are considered as highly effective and include:**

- Combined (estrogen and progestogen containing) hormonal contraception associated with inhibition of ovulation:
  - oral
  - intravaginal
  - transdermal
- Progestogen-only hormonal contraception associated with inhibition of ovulation:
  - oral
  - injectable
  - implantable
- Intrauterine device (IUD)
- Intrauterine hormone-releasing system (IUS)
- Bilateral tubal occlusion
- Vasectomised partner
- Sexual abstinence

**For purpose of this study, acceptable birth control methods which may not be considered as highly effective that result in a failure rate of more than 1% per year include:**

- Progestogen-only oral hormonal contraception, where inhibition of ovulation is not the primary mode of action
- Male or female condom with or without spermicide
- Cap, diaphragm or sponge with spermicide

 Hormonal contraception may be susceptible to interaction with the investigational medicinal product (IMP), which may reduce the efficacy of the contraception method.

 Contraception methods that in the context of this guidance are considered to have low user dependency.

 Vasectomised partner is a highly effective birth control method provided that partner is the sole sexual partner of the WOCBP trial participant and that the vasectomised partner has received medical assessment of the surgical success.

 In the context of this guidance sexual abstinence is considered a highly effective method only if defined as refraining from heterosexual intercourse during the entire period of risk associated with the study treatments. The reliability of sexual abstinence needs to be evaluated in relation to the duration of the clinical trial and the preferred and usual lifestyle of the subject.

 A combination of male condom with either cap, diaphragm or sponge with spermicide (double barrier methods) are also considered acceptable, but not highly effective, birth control methods.

**A woman of childbearing potential (WOCBP) must agree to use 2 methods of acceptable contraception (that are included in the above table in this Appendix 4) with one method highly effective and the other method either highly effective or less highly effective, from the time she signs consent, and until at least 165 days (24 weeks) after her final dose of nivolumab, relatlimab or ipilimumab.**

**A man able to father children who has a female partner of childbearing potential must agree to use 2 methods of acceptable contraception (that are included in the above table in this Appendix 4) with one method highly effective and the other method either highly effective or less highly effective, from the time he signs consent, and until at least 225 days (33 weeks) after his final dose of nivolumab, relatlimab or ipilimumab.**

A woman of childbearing potential participating in the study must have a negative serum pregnancy test during screening and a negative serum or urine pregnancy test  $\leq$  72 hours prior to her first dose of protocol-indicated treatment on Cycle 1, Day 1.

A female is considered to be a “woman of childbearing potential” (WOCBP) following menarche and until becoming post-menopausal unless permanently sterile. Permanent sterilization methods include hysterectomy, bilateral salpingectomy, and bilateral oophorectomy.

Women in the following categories are not considered WOCBP:

- Premenarchal.
- Premenopausal female with 1 of the following:
  - Documented hysterectomy;
  - Documented bilateral salpingectomy;
  - Documented bilateral oophorectomy.

Note: Documentation can come from the site personnel’s review of the participant’s medical records, medical examination, or medical history interview.

A postmenopausal state is defined as 12 months of amenorrhea in a woman over age 45 years in the absence of other biological or physiological causes. In addition, females under the age of 55 years must have a serum follicle stimulating hormone, (FSH) level  $> 40$  mIU/mL to confirm menopause (if menopausal status is considered with respect to contraception required by the study).

Note: Females treated with hormone replacement therapy, (HRT) are likely to have artificially suppressed FSH levels and may require a washout period in order to obtain a physiologic FSH level. The duration of the washout period is a function of the type of HRT used. The duration of the washout period below are suggested guidelines and the investigators should use their judgement in checking serum FSH levels:

- 1 week minimum for vaginal hormonal products (rings, creams, gels);
- 4 week minimum for transdermal products;
- 8 week minimum for oral products.

Other parenteral products may require washout periods as long as 6 months. If the serum FSH level is  $> 40$  mIU/mL at any time during the washout period, the woman can be considered postmenopausal.

Male patients able to father children are defined as those who are not surgically sterile (i.e. patient has not had a vasectomy).

If able to father children, male participants with a female partner of childbearing potential must agree to the following:

---

- Inform any and all partner(s) of their participation in a clinical drug study and the need to comply with contraception instructions as directed by the investigator.
- Inform female partner(s) to consider use of effective methods of contraception until the end of relevant systemic exposure, defined as 225 days after the end of treatment in the male participant.
- Male participants with a pregnant or breastfeeding partner must agree to remain abstinent from penile vaginal intercourse or use a male condom during each episode of penile penetration during the treatment and until 225 days after the end of study treatment.
- Refrain from donating sperm for the duration of the study treatment and until 225 days after the end of study treatment.

A trial physician or clinical designee shall counsel female patients of childbearing potential, and male patients able to father children who have a female partner of childbearing potential, regarding the importance of pregnancy prevention, the implications of an unexpected pregnancy, and the use of acceptable contraception. At a minimum, applicable patients must agree to the consistent and correct use of at least one method of acceptable contraception, as listed in the above table in Appendix 4.

## APPENDIX 5

### ***Response Evaluation Criteria in Solid Tumors (RECIST v1.1)***

#### **Measurability of tumor at baseline**

##### **Definitions**

At baseline, tumor lesions/lymph nodes will be categorized measurable or non-measurable as follows:

##### **Measurable:**

Tumor lesions: Must be accurately measured in at least one dimension (longest diameter in the plane of measurement is to be recorded) with a minimum size of:

- 10 mm by CT scan (CT scan slice thickness no greater than 5 mm).
- 10 mm caliper measurement by clinical exam (lesions which cannot be accurately measured with calipers should be recorded as non-measurable).
- 20 mm by chest X-ray.

Malignant lymph nodes: To be considered pathologically enlarged *and* measurable, a lymph node must be  $\geq 15$  mm in short axis when assessed by CT scan (CT scan slice thickness recommended to be no greater than 5 mm). At baseline and in follow-up, only the short axis will be measured and followed.

##### **Non-measurable:**

All other lesions, including small lesions (longest diameter  $< 10$  mm or pathological lymph nodes with 10 to  $< 15$  mm short axis) as well as truly non-measurable lesions. Lesions considered truly non-measurable include: Leptomeningeal disease, ascites, pleural or pericardial effusion, inflammatory breast disease, lymphangitic involvement of skin or lung, abdominal masses/abdominal organomegaly identified by physical exam that is not measurable by reproducible imaging techniques.

##### **Special considerations regarding lesion measurability:**

Bone lesions, cystic lesions, and lesions previously treated with local therapy require particular comment:

